6.10. Treatment

6.10.1. Drug Supplies, Packaging, and Labeling

ARQ-151 cream or matching vehicle will be supplied in 45 gram tubes. The tubes will be packaged in kits, containing multiple tubes of investigational product. The number of kits dispensed to a subject will be based on the BSA involvement of atopic dermatitis. The kits and tubes will be labeled in a blinded manner. The kit(s) dispensed to a subject will be labeled with a unique number.

The Sponsor will supply sufficient quantities of the study drug and matching vehicle to each site to allow for completion of this study.

Records will be made of the receipt and dispensing of the study drugs supplied. At the conclusion of the study, any used/unused study drugs will be returned to the Sponsor or designee, or destroyed, as per Sponsor instructions.

Refer to the most current version of the IP Handling Plan for details on accountability, storage, and management of ARQ-151.

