6.10.3. Treatment Administration

Initial treatment with the IP will occur on Day 1. ARQ-151 cream 0.05% is administered once daily as a topical product to cover the skin surface at an application rate of approximately 2 mg/cm².

At Baseline visit, the study staff will demonstrate to the parent(s)/caregiver(s) how to apply ARQ-151 cream using the first tube from the kit that is assigned to the subject. Study site staff will be trained to ensure a unit dose (a pea size unit of ARQ-151 cream will cover approximately 1% BSA) is properly squeezed from the tube and applied to atopic dermatitis lesion(s) as a thin film and rubbed in using the index and middle finger, rubbing in thoroughly but gently, until the ‘white’ has disappeared. The parent(s)/caregiver will then practice squeezing a similar amount onto their index and middle finger and apply a thin film to other areas to be treated. At Baseline/Day 1, the study staff will ensure that the parent/caregiver’s application technique is correct and that a thin layer is applied as instructed (which represents an application rate of approximately 2 mg/cm²).

Re-training will be conducted at subsequent visits as needed (i.e., if the returned tube(s) weighs substantially different than the expected weight).

Parents/caregivers will be instructed to apply investigational product once daily to all treatment areas identified by the Investigator at Baseline and any new lesions at subsequent visits using a Body Diagram (see [Appendix 1](#)).

Note:

- All subjects should receive medication each evening (except on clinic visit days when the investigational product will be applied at the clinic). If the subject takes an evening shower/bath, the ARQ-151 cream or vehicle can be applied as soon as the skin is nearly dry, but no later than 20 minutes before going to bed. Subjects are not to wash areas where ARQ-151 cream or vehicle has been applied until at least 4 hours after study drug application.
- Non-medicated emollients or moisturizers will be allowed once daily in a stable regimen as normally used by the subjects. For subjects that apply a non-medicated emollient or moisturizer after an evening shower/bath, the study drug must be applied first to the treatment areas (after the shower/bath). The non-medicated emollient or moisturizer can then be applied but only to other untreated areas of the subject's skin.
- Parents/caregivers should wash their hands with soap and water after applying IP to a child.

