- Parents/guardians/caregivers who are pregnant, or women of childbearing potential who are trying to become pregnant, or who are breastfeeding, or planning to breastfeed during the study should avoid accidental exposure by either avoiding applying investigational product or by wearing gloves during its application.
- Subjects should maintain treatment of areas with study drug for the duration of the study regardless of whether treatable areas of AD clear prior to Week 4 visit.
- New lesions that develop during the study should be treated (except scalp). An unscheduled visit is not required for starting treatment of new lesions.

Each investigational product tube will be weighed prior to dispensing at the Baseline visit and at each subsequent visit. Investigational product tubes must be returned by subjects at each study visit, both empty and full, and will be weighed. If the subject's actual use is substantially different than the expected use for the subject's BSA (see IP Handling Plan), the parent/caregiver will be retrained on the study drug application technique.

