Total weight of study medication applied (determined by weighing the study medication before and after use) will be summarized by treatment using descriptive statistics. Weight of study medication used will be documented in source documents and in eCRF. Total weight of IP used is determined by subtracting minimum of (returned, remained) tube weight from the maximum of (dispensed, prepared) tube weight for each tube that was dispensed and summing the weights. Calculate Actual IP Used: maximum of (dispensed, prepared) tube weight minus minimum of (returned, remained) tube weight = ____ grams

If a tube is not returned at the end of the study or a tube weight is missing, actual IP used for the tube and total weight of IP applied during study will be missing.

Number of days on IP and compliance, including compliance collected at each clinic visit, will be displayed in a listing of study treatment administration by subject, for each treatment. A listing of drug accountability including the kit number, tube number, dispensed and returned weight will also be provided.

 Innovaderm Research ■■■	STATISTICAL ANALYSIS PLAN, Version 1.0
Protocol Number: ARQ-151-315	Sponsor: Arcutis Biotherapeutics, Inc.

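### One unreturned or unweighed tube voids a child's total grams of cream used, so the grams summary may be modestly understated, mainly at the upper end

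*SAP*

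**What the plan says.** SAP section 11 defines the total weight of cream used as dispensed minus returned weight "for each tube that was dispensed and summing the weights". The missing-data rule follows: "If a tube is not returned at the end of the study or a tube weight is missing", then "actual IP used for the tube and total weight of IP applied during study will be missing". The section gives no partial total, bound or sensitivity summary, and no count of children who lose their total by BSA. Protocol section 8.1.4 plans the tube-weight summary by treatment but has no rule for a missing tube.

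Three statements in the protocol bear on how often the rule will apply:

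- Section 6.10.1: "ARQ-151 cream or matching vehicle will be supplied in 45 gram tubes", packed in kits "containing multiple tubes of investigational product".
- Section 6.10.1: "The number of kits dispensed to a subject will be based on the BSA involvement of atopic dermatitis".
- Section 6.10.3: "Investigational product tubes must be returned by subjects at each study visit, both empty and full, and will be weighed".

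Inclusion criterion 7 requires at least 3% BSA and states no upper limit.

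**The concern.** The total needs every tube to be complete, and the number of tubes rises with BSA. Whether a child's total is missing can therefore depend on how much cream the child used. A complete-case summary would then under-represent heavy users, which matters most for the upper quartile and maximum.

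The rule also discards data in hand. When one tube of four is lost, three are fully known, and the fourth may have a weight from Day 8 or Day 15. An unopened tube that is not returned erases the total just as an empty one does.

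What is at stake is the description of how much cream children aged 2-5 years received. Days on treatment and diary applications count days and doses. Tube weight is the only planned measure of grams applied.

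**Working it through.** The documents state no grams used, tubes per child or tube return rate, so there is no figure of the plan's own to reproduce. The check asks how strongly the rule ties missingness to tube count, and what that could do to the mean.

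**Inputs from the documents:** 45 g tubes, several per kit, kits by BSA (Protocol 6.10.1); "cover the skin surface at an application rate of approximately 2 mg/cm²" once daily (Protocol 6.10.3); 28 days (SAP 3.3); BSA of at least 3% (Protocol 6.6.1).

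**Assumed:** total body surface 0.5-0.8 m² (0.6 m² in the simulation); loss per tube q = 1-10%; kits of 2 or 3 tubes; right-skewed BSA with mean about 12% (SD 8) or 22% (SD 18).

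**Step 1, tubes needed.** Grams per 1% BSA = 2 mg/cm² × 1% of body surface × 28 days. At 0.5 m² this is 2 × 50 × 28 = 2,800 mg = 2.8 g. At 0.8 m² it is 2 × 80 × 28 = 4,480 mg = 4.48 g.

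| BSA | Grams over 28 days | 45 g tubes needed |
|---|---|---|
| 10% | 28-44.8 | 1 |
| 20% | 56-89.6 | 2 |
| 50% | 140-224 | 4-5 |
| 80% | 224-358.4 | 5-8 |

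The rule counts tubes dispensed, not tubes needed. Since a kit holds several, a child needing one tube still has at least two at risk, which flattens the gradient at the low end.

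**Step 2, chance of a missing total.** If each of k tubes is lost independently with probability q, P(missing) = 1 − (1 − q)^k. For q = 5% and k = 4: 1 − 0.95⁴ = 18.5%.

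| q | k = 2 | k = 4 | k = 8 |
|---|---|---|---|
| 1% | 2.0% | 3.9% | 7.7% |
| 2% | 4.0% | 7.8% | 14.9% |
| 5% | 9.8% | 18.5% | 33.7% |
| 10% | 19.0% | 34.4% | 57.0% |

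**Step 3, effect on the summary.** One million children per setting were simulated under these assumptions, with full use at the planned rate and no dropouts. At q = 5%:

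| Mean BSA | Tubes per kit | True mean (g) | Complete-case mean (g) | Bias in mean | 90th percentile (g), true → complete-case |
|---|---|---|---|---|---|
| 12% | 2 | 40.31 | 39.82 | −1.2% | 70.1 → 69.0 |
| 12% | 3 | 40.31 | 40.01 | −0.7% | 70.2 → 69.7 |
| 22% | 2 | 72.99 | 70.00 | −4.1% | 139.4 → 131.7 |
| 22% | 3 | 72.95 | 70.54 | −3.3% | 139.3 → 130.8 |

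At q = 1% the bias in the mean is −0.1% to −0.8%; at q = 10% it is −1.2% to −7.8%. The assumed BSA spread drives the result. At q = 5%, a narrow distribution (median 8%, log-SD 0.5) gives less than 0.5%, and a wide one (median 15-20%, log-SD 0.9) gives more than 5%.

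**Step 4, other ways of losing tubes.** If a family returns all tubes or none (5% of children, unrelated to tube count), the bias is nil. If 5-10% of children drop out early, having used less cream, and 30-80% of those lose their total, the bias runs from −3.5% to +3.2% (q = 1-5%, mean BSA 22%, two tubes per kit). The upper figure comes from 10% dropouts, 80% of them missing, with q = 1%.

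**The case against.** A reader might infer that the rule removes the children with the most tubes and so biases the reported exposure downward. The documents do not support this, for four reasons:

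- **Frequency.** Children with more tubes lose their total more often, not always, and only if tubes are lost singly. Step 4 shows that the bias can vanish or reverse.
- **Size.** BSA distribution, tubes per kit and return rate are not given. The only observed mean BSA in the documents is 9.5%, from the Phase 2 study in adults and adolescents with entry capped at 35% (Protocol 4.4.5). A mean that low would put the bias near the bottom of the range.
- **Reach.** Only one descriptive table is touched. Compliance comes from the diary (Protocol 6.10.4). Days on treatment, diary applications and the efficacy analyses do not use tube weights. Amendment 1 removed the Week 4 PK draw, but SAP 14 still provides for a PK report, and Protocol 4.4.4 describes a maximal-use cohort aged 2-5 years on the 0.05% cream.
- **Visibility.** SAP 5.6 reports the number of subjects with each continuous summary, and SAP 11 lists dispensed and returned tube weights.

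All four stand and limit the point. They do not remove it. The number of subjects by arm does not show whether the missing totals cluster at high BSA, and a listing leaves the reader to rebuild the totals.

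A reader might also want grams per treated area compared with the planned rate. Baseline BSA is the wrong denominator for that: palms and soles are treated but not counted (Protocol 7.2.1), and new lesions are treated as they appear (Protocol 6.10.3).

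**Conclusion.** The point holds in a limited form. The rule makes a missing total more likely as tube count, and so BSA, rises, provided tubes are lost singly. The grams-used summary may then be understated, mainly in the upper tail. With independent loss of 5% of tubes and the assumed BSA distributions, the mean is low by roughly 1-4%, and the 90th percentile by up to about 6% (139.3 to 130.8 g). These figures illustrate the mechanism and do not predict this trial's result. The sign is likely downward but not certain. This is a cheap improvement of minor severity and has no bearing on the efficacy conclusions.

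**What to change.** In SAP section 11, keep the complete-case summary and add two items.

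1. Total grams for all treated children under two bounds for each tube without a usable final weight. Lower: use up to that tube's last recorded weight, or 0 g if this cannot be computed. Upper: full contents of the tube. Each such tube widens a child's range by at most 45 g.
2. The number of children with an incomplete total, by arm and by baseline BSA group (below 10% versus 10% or more, already defined in SAP 6.6).

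If the two bounded summaries nearly agree, the issue is shown to be trivial. If they differ, the reader sees by how much and in which BSA group.

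The cost is a few lines of SAP text and one extra table, from weights the protocol already requires at each visit. The downside is that a few totals appear as a range.

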12 EFFICACY ANALYSIS

12.1 Primary Efficacy Endpoint Analysis

12.1.1 Primary Efficacy Endpoint and Estimand

The vIGA-AD is a static evaluation of qualitative overall AD severity. This global assessment scale is an ordinal scale with five severity grades (reported only in integers of 0 to 4). Each grade is defined by a distinct and clinically relevant morphologic description that minimizes inter-observer variability. vIGA-AD is evaluated for the entire body except the scalp, palms, and soles.

The primary efficacy endpoint is vIGA-AD success, defined as an vIGA-AD score of ‘clear’ (0) or ‘almost clear’ (1) plus at least a 2-grade improvement from Baseline at Week 4.

The primary estimand is described by the following attributes:

Population: Patients with Atopic Dermatitis

Endpoint: vIGA-AD success at Week 4

Intercurrent events: In the course of the 4-week randomized treatment period, subjects may be exposed to possible known or unknown intercurrent events that could possibly impact the estimates of the estimand, such as treatment discontinuation due to a specific adverse effect or perhaps a lack of effect. A composite strategy will be implemented that handles subjects who discontinue due to lack of efficacy or adverse event as missing not at random differently than all other subjects. That is, subjects who discontinue due to lack of efficacy or adverse event will be treated as non-responders for all pre-specified analysis visits (refer to Section 5.4) for which the subject’s last dose day falls within the analysis window or is prior to the start of the analysis window (refer to Section 5.5) while the “Treatment Policy Strategy” will be adopted for handling intercurrent events in this study other than discontinuation due to lack of efficacy or adverse event.

Population-level summary: ratio of the odds of achieving vIGA-AD success after 4 weeks of using roflumilast cream 0.05%, relative to the odds of success after 4 weeks using a matching vehicle cream in the ITT population.

The supportive population-level summary: the proportion difference between Roflumilast cream 0.05% and vehicle groups will be provided for the patients who achieve vIGA-AD success at week 4 in the ITT population.

 Innovaderm Research ■■■	STATISTICAL ANALYSIS PLAN, Version 1.0
Protocol Number: ARQ-151-315	Sponsor: Arcutis Biotherapeutics, Inc.

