8.2. Efficacy Evaluation

8.2.1. Statistical Methods

Subjects will be stratified by Baseline vIGA-AD score and by study site, however due to a very low number of subjects in many sites, the analysis model will only stratify by vIGA-AD score stratum.

The primary endpoint will be tested using ITT population.

The primary estimand is described by the following attributes:

Treatment: Roflumilast cream 0.05%

Population: Subjects aged 2-5 years with Atopic Dermatitis

Endpoint: vIGA-AD success at Week 4

Handling of Intercurrent Events: A hybrid strategy will be used for handling intercurrent events. For events other than discontinuation due to AE or lack of efficacy (LoE), the occurrence of the intercurrent event will be considered irrelevant in defining the treatment effect of interest, i.e., the value for the variable of interest is used regardless of whether the intercurrent event occurs. This is the treatment policy strategy. Discontinuation due to an AE or LoE is considered to be informative about the subject's outcome and is incorporated into the definition of the variable. To that end, subjects who discontinue due to LoE or AE will be treated as non-responders for an analysis visit if the study day of the subject's last dose day falls within or prior to the relevant analysis visit window. Analysis visit windows will be defined in the SAP. This is a composite variable strategy.

Population-level Summary: The ratio of the odds of achieving vIGA-AD success after 4 weeks of using roflumilast cream 0.05%, relative to the odds of success after 4 weeks using a matching vehicle cream in the ITT population.

Missing data will be handled with multiple imputation methods (MI). A Cochran-Mantel-Haenszel (CMH) test stratified by the baseline vIGA-AD score used for randomization, will be performed separately for each of the multiply imputed analysis data sets, and results will be combined into one multiple imputation inference. The CMH test will not be stratified by study site as the 650 subjects will be randomized by over 90 sites leading to a low subject to site ratio. The common Mantel-Haenszel (MH) odds ratio and common MH proportion difference, adjusted for baseline vIGA-AD score used for randomization, will be provided along with their associated 97.5% and 95% CIs. Statistical significance will be concluded at the 2.5% significance level (2-sided).

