5.1 Sample Size

Approximately 650 subjects are planned to be randomized in this study. To test the secondary endpoint of IGA success in subjects with a vIGA-AD score of ‘Moderate’ at randomization, approximately 490 of the subjects to be accrued will have vIGA-AD score of ‘Moderate’ at randomization. Randomization will be stratified by vIGA-AD score (‘Mild’ vs. ‘Moderate’), and study site.

This study is designed to differentiate between a vehicle cream treatment that has an IGA success rate of 22% or less and ARQ-151 cream treatment with an IGA success rate of 37% or more. The hypothesis is that the IGA success rate among subjects treated with ARQ-151 cream 0.05% is significantly greater than the IGA success rate among subjects treated with vehicle cream.

This sample size provides more than 90% power to detect 15% difference between treatment groups on vIGA-AD success at Week 4 at $\alpha=0.025$ using a 2-sided stratified Cochran-Mantel-Haenszel (CMH) test. The results from a recent phase 2 study (ARQ-151-212) of ARQ-151 cream 0.05% compared to vehicle treatment were used to estimate the treatment difference. The vIGA-AD success rate at Week 4 was approximately 38% in the ARQ-151 cream 0.05% group compared to 22% in the vehicle. Similarly, approximately 37% of subjects demonstrated vIGA-AD success at Week 4 in the ARQ-151 cream 0.15% group. This sample size also provides more than 80% power to detect an overall 15% difference between treatment groups on IGA success at Week 4 in subjects with vIGA-AD score ‘moderate’ at randomization. The same testing method, the stratified CMH test, will be used as for the primary endpoint.

 Innovaderm Research	STATISTICAL ANALYSIS PLAN, Version 1.0
Protocol Number: ARQ-151-315	Sponsor: Arcutis Biotherapeutics, Inc.

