12.1.2 Hypothesis Testing

Primary hypothesis testing on the odds ratio: The null hypothesis is that the vIGA-AD success does not differ between roflumilast cream 0.05% and matching vehicle cream. The alternative hypothesis is that the vIGA-AD success does differ between roflumilast cream 0.05% and matching vehicle cream.

Null Hypothesis (H_0): $P_R Q_V / P_V Q_R = 1.0$,

Alternative Hypothesis (H_A): $P_R Q_V / P_V Q_R \neq 1.0$, where

P_R = the proportion of vIGA-AD success in roflumilast cream 0.05%

P_V = the proportion of vIGA-AD success in matching vehicle cream

$Q_R = 1 - P_R$

$Q_V = 1 - P_V$.

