12.1.3 Primary Endpoint Analysis

For the primary analysis, missing vIGA-AD scores will be imputed using multiple imputation as described in Section 6.2.1. These imputations will result in a minimum of 25 to a maximum of 250 complete analysis datasets, depending on the number of imputed monotone datasets that are required.

Percentages of subjects having a vIGA-AD Success (refer to Section 12.1.1) will be presented by visit and treatment group based on multiply imputed data in the ITT population along with both 97.5% and 95% Wilson CIs. The common MH odds ratio and common MH proportion difference, adjusted for the randomization factor (i.e., randomized vIGA-AD score) will also be provided along with their common associated 97.5% and 95% CIs. Additionally, count and percentage of subjects having a vIGA-AD success, count and percentage of subjects in each category of the vIGA-AD scale, and descriptive statistics for the vIGA-AD scores, change in vIGA-AD score from baseline and percent change in vIGA-AD score from baseline will be presented by visit and treatment group based on observed data in the ITT population.

The primary endpoint (vIGA-AD Success at Week 4) will then be analyzed using multiple imputation CMH test stratified by randomized baseline vIGA-AD. To do so, a CMH analysis will be performed separately for each of the complete multiply imputed analysis data sets, and results will be combined into one multiple imputation inference using the methodology described in Section 6.2.1. Statistical significance will be concluded at the 2.5% significance level (2-sided). Should the odds ratio be not estimable for at least one multiply imputed dataset, the conclusion of

 Innovaderm Research ■■■	STATISTICAL ANALYSIS PLAN, Version 1.0
Protocol Number: ARQ-151-315	Sponsor: Arcutis Biotherapeutics, Inc.

the study will be based on the p-value obtained from a MH test, stratified by randomized baseline vIGA-AD, for the common MH proportion difference at Week 4.

The following sensitivity and supplemental analyses to the primary analysis of the primary endpoint will be performed:

- Tipping Point analysis (refer to Section [6.2.3](#)) on ITT population.
- Non-responder imputation (refer to Section [6.2.2](#)) on ITT population.
- Observed data on ITT population (refer to Section [4.1](#)).
- Observed data on PP population (refer to Section [4.2](#)).

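### The stated estimand is an odds ratio of overall ITT proportions, but the only primary odds ratio reported is conditional on randomized vIGA-AD stratum

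*SAP*

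**What the plan says.** **Target.** SAP 12.1.1 gives the population-level summary as the "ratio of the odds of achieving vIGA-AD success after 4 weeks of using roflumilast cream 0.05"%, compared with the odds under vehicle, in the ITT population. Protocol 8.2.1 gives the same summary. SAP 12.1.2 states the null as P_R Q_V / P_V Q_R = 1, where P_R is "the proportion of vIGA-AD success in roflumilast cream 0.05"% and P_V is the vehicle counterpart. There is one proportion per arm and no stratum index.

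**Estimate.** SAP 12.1.3 reports "The common MH odds ratio and common MH proportion difference, adjusted for the randomization factor", that is, randomized vIGA-AD score. Protocol 8.2.1 agrees: "The common Mantel-Haenszel (MH) odds ratio and common MH proportion difference, adjusted for baseline vIGA-AD score used for randomization". SAP 6.2.1 combines these quantities over the imputed datasets.

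Neither document says that the estimand is conditional on stratum. Neither plans an unstratified or standardised odds ratio for the main analysis of the primary endpoint. The unstratified option in SAP 12.4 is confined to subgroup analyses in which the odds ratio cannot be estimated. Success percentages by arm and the MH proportion difference, a declared supportive summary, are also reported.

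**The concern.** The parameter as written is a marginal odds ratio, and the estimator targets a within-stratum one. If the stratum predicts outcome, these are different quantities even with perfect balance, and a larger sample does not bring them together.

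The endpoint gives a reason to expect a prognostic stratum. Success needs a score of 0 or 1 and an improvement of at least two grades. A child who starts at Mild (2) must therefore reach 0, while a child who starts at Moderate (3) succeeds at 0 or 1. Protocol 6.2 allows up to a quarter of subjects to be Mild.

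What is at stake is the meaning of the primary effect size and its confidence interval. Taken as the estimate of the stated estimand, the reported odds ratio would usually look a little more favourable than the quantity the plan defined.

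**Working it through.** **1. The plan's own figure.** SAP 5.1 states: "This sample size provides more than 90% power to detect 15% difference between treatment groups on vIGA-AD success at Week 4". It contrasts a "vehicle cream treatment that has an IGA success rate of 22% or less" with an "ARQ-151 cream treatment with an IGA success rate of 37% or more". SAP 12.1.3 sets the level: "Statistical significance will be concluded at the 2.5% significance level (2-sided"). The Protocol synopsis gives about 433 active and 217 vehicle subjects.

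- Pooled rate = (433×0.37 + 217×0.22)/650 = 0.320.
- SE under the null = √[0.320×0.680×(1/433 + 1/217)] = 0.0388.
- SE under the alternative = √[0.37×0.63/433 + 0.22×0.78/217] = 0.0365.
- z = (0.15 − 2.241×0.0388)/0.0365 = 1.73, so power is 95.8%.
- The same calculation for 490 Moderate subjects at 2:1 gives 88.2%.

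Both agree with the stated bounds (more than 90% and more than 80%).

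**2. Population odds ratio.** (0.37/0.63)/(0.22/0.78) = 2.082.

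**3. Relation between the two odds ratios.** Let w be the Mild share. With 2:1 allocation in each stratum:

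- A = P_R Q_V = 0.37×0.78 = 0.2886
- B = P_V Q_R = 0.22×0.63 = 0.1386
- C = w(1−w) × (Mild − Moderate gap, active) × (Mild − Moderate gap, vehicle)
- Population odds ratio = A/B
- MH odds ratio = (A − C)/(B − C)

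Since A > B here, the MH value is larger when C > 0, equal when C = 0 and smaller when C < 0.

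**4. Size if both strata share one odds ratio.** SAP 5.1 plans about 490 of 650 subjects as Moderate, so w = 160/650. The overall rates are held at 22% and 37%. The stratum gaps are assumptions.

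| Vehicle Mild / Moderate | Active Mild / Moderate | MH odds ratio | Ratio to 2.082 |
|---|---|---|---|
| 22.0% / 22.0% | 37.0% / 37.0% | 2.08 | 1.000 |
| 18.2% / 23.2% | 31.8% / 38.7% | 2.09 | 1.002 |
| 14.5% / 24.5% | 26.2% / 40.5% | 2.10 | 1.010 |
| 10.7% / 25.7% | 20.3% / 42.4% | 2.13 | 1.024 |
| 6.9% / 26.9% | 13.9% / 44.5% | 2.18 | 1.046 |
| 29.5% / 19.5% (Mild higher) | 46.8% / 33.8% | 2.10 | 1.009 |
| 37.1% / 17.1% (Mild higher) | 56.0% / 30.8% | 2.16 | 1.038 |
| 44.6% / 14.6% (Mild higher) | 64.6% / 28.0% | 2.27 | 1.090 |

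Example for the fifth row: C = 0.1856×0.200×0.306 = 0.0114, so MH = 0.2772/0.1272 = 2.18. The proportion difference weighted by stratum size is 15.0 points in every row.

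Extreme case with Mild lower, at 25% Mild: vehicle 2% Mild and (0.22 − 0.25×0.02)/0.75 = 28.7% Moderate, a gap of 27 points. The active rates are then 4.5% and 47.8%, C = 0.1875×0.267×0.434 = 0.0217, and MH = 0.2669/0.1169 = 2.28, about 10% above 2.08.

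**5. Unequal stratum odds ratios, w = 160/650.**

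- Same ordering in both arms: vehicle 10% / 26%, active 25% / 41% (stratum odds ratios 3.00 and 1.98). Population 2.08, MH 2.12.
- No gap in one arm: vehicle 10% / 25.9%, active 37% in both strata. C = 0, so both are 2.08.
- Reversed ordering: vehicle 30% / 19.4%, active 32% / 38.6%. C = 0.1856×(−0.066)×0.106 = −0.0013, so MH is 2.07 against 2.08.

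**6. Against sampling error.** SE of the log odds ratio, unstratified, = √[1/(433×0.37) + 1/(433×0.63) + 1/(217×0.22) + 1/(217×0.78)] = 0.192. The approximate 97.5% CI is 2.082 × exp(±2.241×0.192), or 1.35 to 3.20. The extreme case moves the estimate by ln(2.283/2.082)/0.192, about 0.5 SE.

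**7. The test.** (A − C)/(B − C) = 1 exactly when A = B, so both odds ratios equal 1 together and the CMH test addresses the stated null.

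**The case against.** The case against has real force.

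- The odds ratio is described as adjusted for randomized vIGA-AD wherever its estimation is specified, and Protocol 8.2.1 puts estimand and estimator in one section. The estimand text never says marginal, so it could be shorthand for the analysis beside it. That reading is possible, but the unsubscripted arm proportions in SAP 12.1.2 point the other way, and an estimand should not need inference.
- Much of the missing information will be available. A reader can form the population point estimate from the arm percentages, the proportion difference is collapsible, and SAP 6.6 and 12.4 plan results by randomized vIGA-AD score with forest plots. This stands, except that no confidence interval for the population odds ratio is planned.
- No decision on efficacy changes. This stands in full.

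A reader might infer more than the documents support:

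- **That the MH odds ratio must be the larger one whenever stratum rates differ, or that the two agree only when the strata have equal rates.** Step 5 gives counterexamples. Those statements need a common odds ratio across strata, which neither document asserts.
- **That a 10% inflation is to be expected.** It needs an assumed stratum gap of nearly 30 points. The endpoint rule makes some gap plausible but does not fix its size.
- **That the p-value, type I error or power is at fault.** Steps 1 and 7 show that they are not.

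**Conclusion.** The mismatch is real and minor. The plan states one parameter and reports an estimate of another. The reported odds ratio will usually be slightly further from 1 than the population value: about 1% to 5% at the planning rates, for assumed stratum gaps of roughly 9 to 20 points and a common stratum odds ratio. It can be equal, or slightly smaller, under the conditions in step 5.

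These sizes rest on assumed stratum rates, since the documents give none, and on the same 2:1 ratio holding in both strata. Even the extreme case lies well inside the expected 97.5% CI. The issue is which quantity the primary effect size estimates; the evidence for an effect does not depend on it.

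**What to change.** Keep the CMH test and the MH odds ratio, and label the latter in SAP 12.1.3 as conditional on randomized vIGA-AD. Add the population odds ratio there as the estimate of the stated estimand:

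1. In each imputed dataset, compute each arm's success proportion standardised to the ITT mix of randomized vIGA-AD, p* = Σ w_s p_s.
2. Form the log odds ratio of the two p*. Its delta-method variance is the sum over arms of Var(p*)/[p*(1 − p*)]², with Var(p*) = Σ w_s² p_s(1 − p_s)/n_s.
3. Combine by Rubin's rule and back-transform, with 97.5% and 95% CIs.

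Alternatively, redefine the summary and the null in SAP 12.1.1–12.1.2 and Protocol 8.2.1 as the common odds ratio within randomized vIGA-AD strata. That changes no number and no programming.

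The first option costs one extra derived estimate with its variance, usually slightly less favourable than the MH value. The second costs about a sentence in each document. Neither touches the test, alpha, sample size or proportion difference.
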